10.5. Visit 3 Day 180 (Vital Status Assessment)

The participant will be followed-up by telephone at 180 to 195 days after hospital admission to assess vital status at Day 180 (ie, alive or dead). If investigator is definitively aware of vital status through other means (eg, access to vital statistics records or patient visit in electronic record after Day 180), this source may be used to determine vital status in lieu of a phone call. RRIs will be collected if encountered during the collection of vital status or if the patient is contact by phone.

The following data will be recorded:

- Vital Status at 180 days after admission (ie, deceased or living), including date and cause of death if deceased.
- Information to calculate Charlson Comorbidity Index (diagnosis codes such as International Classifications of Diseases [ICD] discharge codes may be provided as a separate file linked by participant number to calculate CCI or data will be collected via eCRF at this or prior visit).
- Record RRIs per Section 16.2 and selected exposures and AEs related to Pfizer products per Section 16.3.

11 ASSESSMENTS

Collection of clinical data. The study staff will complete a eCRF for each participant at each visit, as detailed above. The eCRF will be completed reviewing the medical records of the patient, the results of the tests performed, and interviewing the participant. Once the eCRF is completed, it will be signed and dated by the investigator verifying the information contained therein.

11.1. Additional Research

Not applicable.

11.2. Biological Samples 11.2.1. Blood and Respiratory Samples

All blood and respiratory specimens collected as part of SOC for culture (eg, blood, pleural fluid, transtracheal aspirate, bronchoalveolar lavage or other respiratory tract specimen) will undergo bacterial culture at the local site laboratory for the identification of SP according to their standard methodology. Best practices for blood culture collection involved obtaining 2 sets of blood cultures before antibiotic administration if possible. The blood culture should be collected and timed according to the local institution's policy using different sampling sites. Anaerobic and aerobic samples should be collected.

Whenever possible, blood should be collected from peripheral veins. Results of blood cultures (including antibiotic susceptibility) from this SOC bacterial culture testing will be recorded in the eCRF.

For sputum specimens collected as part of standard –of care testing, specimen quality will be assessed using the specimen's standard –of care Gram stain results. Only bacterial culture results from high-quality sputum specimens will be use in case categorisation for the VE analysis, but all pneumococcal isolates will be serotyped regarding of specimen quality.

Serotyping, Antimicrobial Resistance and Molecular Biology Testing of the Isolates

Pneumococcal bacterial isolates from SOC specimens will be shipped and analyzed in the Pneumococcal Reference Laboratory from the Centro Nacional de Microbiología which belongs to the Instituto de Salud Carlos III (ISCIII). In no case will there be any interference with the autonomous regional pneumococci monitoring systems at the sites participating in the study.

The ISCIII reference laboratories provide data and information of sanitary interest on the microorganisms that cause infectious diseases, environmental pollutants situation and the development of new technologies and/or surveillance strategies and control in accordance with the priorities established by the Ministerio de Sanidad, Consumo y Bienestar Social (MSCBS) following the recommendations of the European Centre for Disease Prevention and Control (ECDC). The pneumococcal reference laboratory is located in Majadahonda which is a city in Madrid region, it carries out a passive surveillance and receive the isolates from hospitals of all the Spanish regions.

Identification and Serotyping

All isolated pneumococcal strains will be stored frozen in skimmed milk at a temperature of -40°C or lower in the Department of Microbiology of each participating site until delivery to the reference laboratory (RL) at ISCIII. From a fresh culture (18-24h) in blood agar a dense suspension will be obtained (all plate growth will be recorded) in a vial with 0.5 ml of sterile skimmed milk (Skim Milk, Oxoid). The vial will be immediately frozen at -40°C.

The pneumococcus strains should be frozen as soon as possible and with the minimum number of runs.

PFIZER CONFIDENTIAL CT45-GSOP-RF152.0 Low-Interventional Study Protocol Template 05-Dec-2019 Page 42 of 70

The strains will be thawed in the site where they are isolated before being sent at room temperature to the RL. The strains may be sent in the following ways:

• On blood agar plates or tubes, after abundant seeding (without incubation).

Incubation will be performed on reception at the RL. If plates are used, only one strain should be seeded per plate.

• Transport media tubes are preferable. The whole quantity of a fresh culture should be collected from a blood agar plate by dragging with a swap and sent at room temperature in the transport media.

To prevent the loss of strains for reasons of viability during transportation, or other reasons, the microbiology laboratory of each site will keep a frozen sample for up to 6 months for study purposes. The frozen vials, plates or the tubes with transport medium will be identified by the site personnel using a label containing a study code and the subject identifier (site no. and participant no.) from which the isolate comes. In addition, a copy of the label containing the same codes used to identify the isolate will be attached to the study form for submission of strains to the RL. When preparing the pack with the strains, the safety rules applicable in Spain will be followed and standardised packages will be used. Strains will be sent to the ISCIII at regular intervals (every 1-2 months, depending on the volume of strains) using a courier service. Once the samples/strains have been received at the ISCIII a subculture will be performed in the appropriate medium (blood agar or chocolate agar) in order to ensure the viability and purity of the organisms.

For pneumococcal serotyping at the ISCIII, it will be used the Capsular Sequence Typing (CST) methodology.¹⁶ The CST is a well-established molecular method to genotype the capsular locus in order to assess the serotype. It has been accepted as a generic method for typing SP among the different European Pneumococcal Reference Laboratories that belong to ECDC through the Invasive Bacterial Disease network (IBD-labnet). The primers used in the CST are based on the publicly available sequences of the capsular genes of the more than 90 known pneumococcal serotypes.¹⁷ Capsular Sequence Typing (CST) is based on a part of the sequence of the wzh gene of the capsular locus. The 3 forward and 4 reverse primers used in the CST are based on the publicly available sequences of the capsular genes of the 90 known pneumococcal serotypes described by Bentley et al.¹⁷ The primers contain an M13-tail, which facilitates sequencing with universal M13-primers. After sequencing of 506 base pairs of the wzh gene, a capsular type can be assigned. The capsular type is a composite assignment; the first part of the assignment is based on the phenotype assessed by conventional serotyping and the second part of the assignment is the consecutive number of the capsular type belonging to the same serotype.

Antimicrobial Susceptibility Testing

The measurement of the minimum inhibitory concentration (MIC) of each isolate will be performed at the using a broth microdilution method (Sensititre,Trek Diagnostic Systems

PFIZER CONFIDENTIAL CT45-GSOP-RF152.0 Low-Interventional Study Protocol Template 05-Dec-2019 Page 43 of 70

LTD, East Grinstead, United Kingdom) according to the The European Committee on Antimicrobial Susceptibility Testing (EUCAST)² guidelines. For pneumococci Cation-Adjusted Mueller-Hinton Broth (CAMHB) broth will be used, with 2.5-5% lacquer horse blood (LHB). The following antimicrobials will be evaluated: penicillin, amoxicillin, cefotaxime, erythromycin, clindamycin, tetracycline, and levofloxacin.

² http://www.eucast.org/clinical_breakpoints/.

The laboratory investigator of the ISCIII or designee will be responsible for completing a record with the results of serotyping and susceptibility to be submitted to the sponsor regularly. These records will not include any personal data of the participants from whom the isolates were obtained.

11.2.2. Detection of Serotype-specific Pneumococcal Urine Antigen and BinaxNOW®

UAD 1 and UAD 2. The Pfizer UAD is a multiplex immunoassay, based on the Luminex xMAP bead technology, with the ability to combine multiple spectrally distinct microspheres, each conjugated to a different serotype-specific monoclonal antibody in a single well to allow the detection of all antigens simultaneously using only a small volume of urine sample. The 13 serotypes (1, 3, 4, 5, 6A, 6B, 7F, 9V, 14, 18C, 19A, 19F, 23F) covered in the validated UAD 1 assay are the 13 polysaccharide antigens used in Pfizer's 13vPnC vaccine. The UAD 2 assay, using the same Luminex xMAP bead technology detects 11 additional serotypes (2, 8, 9N, 10A, 11A, 12F, 15B, 17F, 20, 22F, 33F).

BinaxNOW[®] SP test is a commercially available, Food and Drug Administration (FDA) approved assay for the detection of SP in the urine and cerebrospinal fluid (CSF) from patients with pneumonia or meningitis. The *BinaxNOW*[®] SP test is an in vitro rapid immunochromatographic test intended to be used in conjunction with culture and other methods, to aid in the diagnosis of pneumococcal pneumonia.

Aliquots for urine samples for testing conducted by Pfizer Inc will be processed and kept frozen in an appropriate local laboratory and will be shipped in bulk for analysis at the Pfizer Vaccines Research and Development (VRD) laboratory, Pearl River, New York, USA. Details regarding sample processing and shipping are provided in a separate laboratory manual. Residual samples from urine aliquots sent for UAD/*BinaxNOW*[®] testing may be stored for future testing at Pfizer laboratories and may be kept for up to COL after the study ends, at which time they will be destroyed. In addition to testing for this study, any residual urine from these aliquots left over after the study is complete may be used for additional research related to the development of products. Pfizer will not perform any testing of genetic material. Residual urine samples at Pfizer may be shared with other researchers as long as confidentiality is maintained, and no testing of the participant's genetic material is performed.

11.2.3. Pneumococcal Carriage and RSV Infection Testing

The saliva samples will be placed in individual bags for transport and will be kept at room temperature until delivery. Samples will be delivered once or twice a week (preferably at the beginning of the week; Mondays or Tuesdays) to improve the culture efficiency. The samples will be referred to the ISCIII for conventional culture and molecular biology study (for culture-negative samples). Briefly, swabs with the saliva samples will be streaked onto blood agar plates containing gentamicin to select SP and avoid the growth of bacteria from the microbiota. For culture-negative samples, characterization of SP will be performed through a real-time PCR assay for the detection of pneumococcus target genes *lytA* and *piaB*. Once pneumococcus is confirmed, a CST methodology will be used to identify the serotype.

PFIZER CONFIDENTIAL CT45-GSOP-RF152.0 Low-Interventional Study Protocol Template 05-Dec-2019 Page 45 of 70

Additional PCR testing for RSV will be performed on the same saliva sample.

The PI of the ISCIII or designee will be responsible for completing a record with the results of the microbiological tests on the nasopharynx to be submitted to the sponsor regularly. These records will not include any personal data of the participants from whom the isolates were obtained.

11.3. Imaging Assessments - Chest Radiography

Patients hospitalised with CAP who have chest imaging studies normally performed as standard care (eg, CXR, CT, magnetic resonance imaging [MRI)]). Results of all imaging performed for this episode of CAP will be recorded on the eCRF. Radiologist review and interpretation will be documented on the eCRF. Radiologically confirmed CAP will be those considered to have a radiologic finding that is consistent with pneumonia (eg, pleural effusion, increased pulmonary density due to infection, the presence of alveolar infiltrates [multilobar, lobar or segmental] containing air bronchograms).

12. DATA ANALYSIS/STATISTICAL METHODS 12.1. Study Size

12.1.1. Defining Cases and Test-negative Controls

For the analysis of the primary endpoint, we will define cases as events involving hospitalised for CAP in whom PCV13 serotypes are identified by any method including UAD1 or routine culture of blood, pleural fluid, or other high-quality respiratory tract specimen. PCV13 VT serotypes are as follows: 1, 3, 4, 5, 6A, 6B, 7F, 9V, 14, 18C, 19A, 19F and 23F. Only sputum isolates from high-quality specimens (see Section 11.1) will be considered in assigning case status. All other episodes of CAP that met the inclusion criteria for the study, but for whom PCV13 or related serotypes are not identified from any source (ie, non-vaccine type [NVT] only) will serve as test-negative controls. Subjects with vaccine-related serotypes (eg, 6C) will be excluded from controls for the primary analysis. Subjects with VT serotype who also have an NVT or vaccine-related serotypes will be classified as cases. Subjects may only contribute one CAP event to any given VE analysis.

For PPV23 VE, cases will be those with one of 23 serotypes in PPV23: 1, 2, 3, 4, 5, 6B, 7F, 8, 9N, 9V, 10A, 11A, 12F, 14, 15B, 17F, 18C, 19A, 19F, 20, 22F, 23F, and 33F (including those where a NVT or vaccine-related serotype is also identified). Events with vaccine-related serotypes (either alone or in combination with an NVT) will be excluded from the controls for the primary analysis. Controls will be those with only nonvaccine serotypes (ie,

all other serotypes). Subjects with VT serotype who also have an NVT or vaccine-related serotypes will be classified as cases.

In sensitivity analyses, we will estimate PCV13 and PPV23 VE using different control group. In this case, controls will be defined as non-VT pneumococcal CAP (Broome method).¹³ That is, controls will be patients in whom pneumococcus is detected by blood/pleural/high-quality sputum culture, *BinaxNOW*[®], or UAD1/2 positive; but VT or vaccine-related serotypes are not identified from culture or UAD1/2. (ie, serotypes identified are not VT or related serotypes). In the second sensitivity analysis, we will define controls as CAP patients in whom pneumococcus was not detected by any method (culture, UAD, or *BinaxNOW*[®]), similar to a recently published TND.¹⁴

If PCV20 use is initiated in the surveillance area during the study, PCV20 vaccinated persons would be excluded from both case and control groups for the PCV13 VE analysis.

12.1.2. Study Size Estimates

The required sample size depends on the accrual of immunocompetent VT-CAP cases, the VE point estimate, percentage of individuals vaccinated, as well as other factors. Based on calculations outlined below in detail, the overall number of subjects to be enrolled is expected to be between 2,000 and 5,500 and will require between 1.7 and 4 years of enrolment period.

Hospitalised pneumonia cases have been forecasted here based on the incidence of all-cause hospitalised CAP in the Madrid Region derived from the Spanish *Conjunto Mínimo Básico de Dato* (CMBD)

(https://pestadistico.inteligenciadegestion.mscbs.es/publicoSNS/comun/ArbolNodos.aspx) for the year 2015. CMBD is the Spanish centralized hospital discharge database that covers nearly the entire Spanish population and includes more than 95% of admissions to hospitals of the National Health System, thus providing a complete record of all hospitalisations at National level and by Region. To estimate the incidence of hospitalised pneumonia cases in adults 60 years and older, we use the seven ICD-9 codes for pneumonia (480, 481, 482, 483, 484, 485 and 486) that resulted in 22,487 hospitalisations per year with an incidence rate of 1.5 per 100 adult older than 60 years in the Region of Madrid (Table 4).

Table 4.Incidence of Hospitalised Pneumonia Cases in Adults 60 Years and Older

Madrid Region, CMBD 2015 ^a	60-64y	65-74 y	>74y	Total Cases/Incidence rate per 10 ⁵
480–viral	9	25	37	71/4.98
481-pneumococcal	110	345	1192	1,647/115.53
482-Other bacteria	96	316	707	1,119/78.49
483-Other organism	7	13	20	40/2.81
484-Other	17	36	53	106/7.44
485-Broncopneumonia	52	136	583	771/54.08
486-Non specify	1,094	3,508	14,131	18,733/1,314
Total	1,385	4,379	16,723	22,487/1,577.37

a. The ICD codes in this column as well as 487.0, 510, 513 will be used to retrospectively screen for missed CAP events to ensure completeness of surveillance.

The equivalent codes for hospitalised pneumonia under ICD-10 (Table 5) are as follows:

ICD-10 codes ^a	
J12	Viral pneumonia, unspecified
J09.X1	Influenza due to identified novel influenza virus with pneumonia
J10.00	Influenza due to other identified influenza virus with unspecified type of pneumonia Influenza due to other identified influenza virus with the same other identified influenza virus
J10.01	pneumonia. Influenza due to other identified influenza virus
J10.08	with other specified pneumonia.
J11.00 J11.01	Influenza due to unidentified influenza virus with unspecified type of pneumonia. Influenza due to unidentified influenza virus with other respiratory manifestations. Influenza due to unidentified influenza virus with specified pneumonia.
J11.08	
J13	Pneumonia due to Streptococcus pneumoniae
J14	Pneumonia due to Hemophilus influenzae
J15	Unspecified bacterial pneumonia
J16	Pneumonia due to other infectious organisms, not elsewhere classified
J17	Pneumonia in diseases classified elsewhere
J18	Bronchopneumonia, unspecified organism

Table 5.Codes for Hospitalised Pneumonia Under ICD-10

a. The ICD codes in this column as well as J1100, J129, 5100, 5109, and 5130 will be used to retrospectively screen for missed CAP events to ensure completeness of surveillance.

For this study surveillance region, we expect approximately 1800 all-cause CAP patients in the age group of the study are hospitalised yearly based on 2018 data. This would represent 162 PCV13-type cases per year overall considering 9% of VT-CAP cases as per the CAPA study¹ and 648 PCV13-type cases in 4 years of expected duration of the study. Approximately, 36% of CAP admissions are expected to be immunocompromised persons, so we expect ~104 immunocompetent CAP cases annually (~416 over 4 years).²⁰ The following table (Table 6) estimates accrual of cases and controls for the VE analysis for immunocompetent subjects varying the key inputs. For these calculations, 2.5% alpha was used to split alpha allocated between interim analysis and final analysis (ie, 2.5% to each analysis).

Scenario input vari	.,	Vaccine Coverage Among Controls	Projected Vaccine Effectiveness	Vaccinetype (VT) Serotype Prevalence	Case:Control Ratio based on VT Serotype Prevalence	Needed Cases	Expected non-VT Controls	Total Evaluable subjects	Enrolled,⁵ n	% CAP inpatients enrolled	CAP inpatients needed, ^c n	Years to Enroll ^d
Expected	1	15%	70%	9%	1:10	117	1165	1282	1349	70%	1928	1.7
VE	2ª	15%	60%	9%	1:10	170	1692	1862	1960	70%	2800	2.4
	3	15%	50%	9%	1:10	259	2584	2843	2993	70%	4275	3.7
_	4	15%	40%	9%	1:10	427	4261	4688	4935	70%	7050	6.1
% CAP	5	15%	60%	7%	1:13	167	2160	2327	2449	70%	3499	3.0
VT	6	15%	60%	11%	1:8	173	1380	1553	1635	70%	2335	2.0
	8	15%	60%	13%	1:7	176	1224	1400	1474	70%	2105	1.8
% Vax	9	10%	60%	9%	1:10	252	2516	2768	2914	70%	4162	3.6
% VdX	10	20%	60%	9%	1:10	129	1283	1412	1486	70%	2123	1.8
90% Power	11	15%	60%	9%	1:10	208	2070	2278	2398	70%	3426	3.0
%	12	15%	60%	9%	1:10	170	1692	1862	1960	50%	3920	3.4
enrolled	13	15%	60%	9%	1:10	170	1692	1862	1960	30%	6533	5.7

Table 6.Sample Size Scenarios for VE Calculations At Interim

- a. Base case values are highlighted in gray; 2.5% alpha was used for all scenarios and 80% power was used for all scenarios except #11. All calculations done with OpenEpi, Version 3, open-source calculator (Sample Size-Unmatched Case Control Study; available @ https://www.openepi.com/SampleSize/SSCC.htm) and used Fleiss method with continuity correction, which is consistent with estimates based on Fischer's exact test. For these calculations, 2.5% alpha was used to split alpha allocated between interim analysis and final analysis (ie, 2.5% to each analysis).
- b. Includes projected 5% of subjects with no valid pneumococcal serotype specimen result.
- c. Number of "CAP inpatients needed" is based on the percentage of CAP patients enrolled in prior column, which accounts for loss of potential subjects who declined participation or were not offered participation due to incomplete surveillance.
- d. Estimate 1800 CAP admissions annually in the surveillance area and 36% would be immunocompromised, leaving ~1150 immunocompetent CAP admissions annually and ~104 vaccine-type pneumococcal CAP cases.

In conclusion, assuming 9% VT-CAP, Scenario 1 sample size would be reached in 1.7 years after enrolling 1349 immunocompetent subjects (~2107 subjects overall), Scenario 2 (base case) in 2.4 years after enrolling 1960 immunocompetent subjects (~3063 subjects overall), and Scenario 3 in 3.7 years after enrolling 2993 subjects (~4,677 subjects overall). An increase in percentage of cases that VT-serotype to $\geq 11\%$ or the vaccinated proportion to 20% would reduce the time to accrue the needed cases for the interim analysis to 2 years or less. Lower proportion of VT-serotypes, lower VE point estimate, lower percentage of PCV13-vaccinated persons, or lower number of patients enrolled or subjects with valid urine specimens could all increase the time to achieve the needed number of vaccine serotype CAP cases. As the required number of enrolled subjects is highly dependent on the proportion of CAP subjects that have VT pneumococcal CAP and the proportion of the population vaccinated, the required sample size may be adjusted based on ongoing information from UAD testing results and vaccine exposure data if needed. An interim analysis will be conducted after accrual of 170 VT-cases (scenario 2 above), but, given additional subjects may be needed to allow for adequate statistical power, 4 years of enrolment is planned, which would bring the number of subjects enrolled to 5,400 (based on 1,800 potential subjects annually and 70% enrolled).

If the anticipated PCV20 is approved during the enrolment of cases for VE analysis as

expected (projected to be in use no sooner than late 2022), subjects with PCV20 exposure will be excluded from both the cases and the controls for the PCV13 VE analysis. We expect substantial number of persons with a history of PCV13 vaccination to remain in the population in this age group and, thus, event accrual for VE analysis would not be significantly impact immediately following the PCV20 launch.

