9. RESEARCH METHODS

9.1. Study Design

This is a low interventional, prospective, multicentre, hospital- based study in adults aged 60 years of age and older hospitalised with CAP at participating sites. Hospital surveillance data will be used for incidence calculations and a TND for VE calculations. Vaccine effectiveness will be calculated using a TND. The approximate study duration will be 4 years.

In the South of Madrid there are two municipalities that belong to the network of King Juan Carlos I University (Figure 1):

Móstoles is a city located in the southwest of the Madrid region. Its total population is 210,309 people,¹² 57,042 of them are people aged 60 years or older. For secondary care, the population that receives medical care at the Hospital Universitario de Móstoles includes 137,552

PFIZER CONFIDENTIAL CT45-GSOP-RF152.0 Low-Interventional Study Protocol Template 05-Dec-2019 Page 27 of 70

inhabitants which represents 65.4% of the total population of the town. There is another hospital, Hospital Universitario Rey Juan Carlos included in the study in February 2022, that covers the remaining population. The Hospital Universitario de Móstoles has 332 beds, while the Hospital Universitario Rey Juan Carlos has 358 beds.

Alcorcón is a city located in the Southwest of Madrid region. Its total population is 172,384 people,¹² 45,535 of them are people of 60 years or older. The population receives medical care at its only hospital, called Hospital Universitario Fundación Alcorcón, which is the only public hospital in Alcorcón. The hospital has 400 beds.

As of 1st January 2020, the total population of these two municipalities (Alcorcón and Móstoles) was 382,693 people, 103,844 of them were of 60 years and older that represents 6.5% of the total population of Madrid Region (in total: 1,593,526 inhabitants in this age group) (Table 3). In Spain, every town or village is obliged by law to maintain and update the census ("padrón municipal de habitantes"). An automated and electronic population registry is continuously updated (eg, with new people registering, leaving the village, or dying). Thus, these population denominators are not intercensus extrapolations but actual counts. An internal audit of the population by [name] has shown the populations are comparable to the averages across Spain.

[figure not shown]

Table 3. Population of Adults 60 Years and Older Living in Participating Hospitals'Geographic Catchment Area (January 2020)

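### The 1,800 CAP admissions a year behind Table 6's accrual times is not reconciled with the protocol's own rate and population, and the 648 and 416 cases are counted before enrolment loss

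*Protocol*

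**What the plan says.** Protocol 12.1.2 opens by basing the forecast on 2015 hospital-discharge data for the Madrid Region, "with an incidence rate of 1.5 per 100 adult older than 60 years in the Region of Madrid". The Table 4 total reads "22,487/1,577.37" (cases, and rate per 100,000).

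For the study area the same section then states that "we expect approximately 1800 all-cause CAP patients in the age group of the study are hospitalised yearly based on 2018 data". It names no source, hospital list or calculation. Section 9.1 gives the population of the two municipalities: "103,844 of them were of 60 years and older that represents 6.5% of the total population of Madrid Region".

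From 1,800 the section derives 162 vaccine-type (VT) cases a year and 648 in 4 years. After removing 36% as immunocompromised it says "so we expect ~104 immunocompetent CAP cases annually (~416 over 4 years". Footnote d of Table 6 turns 1,800 into about 1,150 immunocompetent admissions a year, the divisor for Years to Enroll. Footnote b describes the Enrolled column: "Includes projected 5% of subjects with no valid pneumococcal serotype specimen result". The text concludes "Scenario 3 in 3.7 years after enrolling 2993 subjects" (VE 50%), with 4 years of enrolment planned.

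**The concern.** The rate presented as the basis of the forecast and the stated population do not give 1,800. Every entry under Years to Enroll rests on that number, as do the 1.7 to 4 year range and the expected interim date in section 12.5. The VE 50% scenario sits close to the planned 4 years, so a shortfall of about a tenth matters there.

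Three further features make the forecast hard to use:

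- The figure is flat over time, although section 9.1 says the second Móstoles hospital joined only in February 2022 and data collection began in March 2021.
- The 648 and 416 are on a different basis from the needed cases in Table 6. A reader who sets 416 beside the 259 needed for VE 50% sees a margin that is mostly not there.
- The Enrolled column allows only for invalid specimens. Section 12.1.3.1 also removes final diagnoses other than CAP, pneumococcal vaccination in the previous 30 days, less than 5 combined years of vaccination history, and PCV20 recipients.

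**Working it through.** **1. Reproducing Table 6.** Scenario 3 has coverage among controls p0 = 0.15, OR = 0.5, r = 10 controls per case, two-sided alpha 0.025 and 80% power.

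- p1 = OR·p0 / (1 − p0 + OR·p0) = 0.075/0.925 = 0.0811; pooled p = (p1 + r·p0)/(r + 1) = 0.1437.
- Without correction: n' = [2.2414·√((r+1)·p(1−p)) + 0.8416·√(r·p1(1−p1) + p0(1−p0))]² / [r(p1−p0)²] = 242.5.
- Fleiss continuity correction: n = (n'/4)·[1 + √(1 + 2(r+1)/(n'·r·|p1−p0|))]² = 258.3, so 259 cases, as stated.
- Evaluable 2,843 / 0.95 = 2,993 enrolled; / 0.70 = 4,275 inpatients; / 1,150 = 3.7 years.

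All 12 rows reproduce, cases to within 1 and years to rounding. The 70% and the 5% are therefore already in the times.

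**2. Reproducing 648 and 416.** 1,800 × 0.09 × 4 = 648. 1,800 × 0.64 × 0.09 = 103.7, rounded to 104; × 4 = 416. Both are correct as counts of admissions, and neither enters Years to Enroll.

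**3. Admissions from the stated rate and population.** The municipal figures in section 9.1 sum to 57,042 + 45,535 = 102,577. The stated total of 103,844 equals 57,042 + 46,802, the second number being Table 3's figure for Alcorcón. The rate is 1,577.37 per 100,000 (Table 4) or 1.5 per 100 (text). Years = inpatients needed / (admissions × 0.64), with 2,800 inpatients for the base case and 4,275 for VE 50%. Evaluable immunocompetent VT cases in 4 years = admissions × 0.64 × 0.09 × 0.70 × 0.95 × 4.

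| Admissions a year | Basis | Evaluable cases, 4 years | Base case, years | VE 50%, years |
|---|---|---|---|---|
| 1,800 | stated | 276 | 2.4 | 3.7 |
| 1,638 | 1,577.37 per 100,000 × 103,844 | 251 | 2.7 | 4.1 |
| 1,618 | 1,577.37 per 100,000 × 102,577 | 248 | 2.7 | 4.1 |
| 1,558 | 1.5 per 100 × 103,844 | 239 | 2.8 | 4.3 |
| 1,539 | 1.5 per 100 × 102,577 | 236 | 2.8 | 4.3 |

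1,638/1,800 = 0.91 and 1,539/1,800 = 0.855, so the rate-based count is 9-15% lower. Reaching 1,800 would need 114,114 residents at the Table 4 rate or 120,000 at 1.5 per 100. Break-even for VE 50% in 4 years is 4,275 / 4 / 0.64 = 1,670 a year. With 236-251 cases, power at VE 50% is about 75-78% by the same corrected formula at alpha 0.025.

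**4. Third hospital phased in.** Table 3 gives 35,106 + 46,802 = 81,908 for the first two hospitals. Take 11 months on 81,908, then 103,844.

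- Table 4 rate: 1,292 × 11/12 + 1,638 × 37/12 = about 6,235 admissions in 4 years and 239 evaluable cases; base case 2.9 years, VE 50% 4.3.
- 1.5 per 100: about 5,929 admissions and 227 cases; 3.0 and 4.5 years.
- If 1,800 is the three-hospital total (an assumption): 1,800 × 81,908/103,844 = 1,420 for 11 months, then 1,800, giving about 262 cases; 2.6 and 3.9 years.

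Even on the two-hospital catchment throughout (1,229 to 1,292 a year), the base case takes 3.4-3.6 years.

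**5. The 648 on the evaluable basis.** 648 × 0.70 × 0.95 = 431 in all patients. At 1,539 to 1,638 a year it is 368 to 392.

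**6. Other exclusions.** The documents give no size. If 10-20% of enrolled patients were lost to them (assumption), the base case would need 1,960/0.90 = 2,178 to 1,960/0.80 = 2,450 immunocompetent subjects. Losses to a non-CAP final diagnosis raise the headcount but do not lengthen the time, because Years to Enroll starts from CAP admissions.

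**The case against.** The strongest defence is that 1,800 is a different measurement, not a product of the rate. It is attributed to 2018 and to the surveillance region, while Table 4 is 2015, region-wide, and built on seven ICD-9 codes. The ICD-10 list in Table 5 names influenza pneumonia separately. 1,800/103,844 is 1.73 per 100, and a gap of this size between years and areas is plausible. The rate-based figure also counts residents only. Version 3.0 removed the residence criterion, and more sites may be added. All of this stands: 1,800 is unreconciled, not disproved, and 1,638 should not replace it as fact.

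Three stronger readings are tempting, and the documents do not support them.

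- *Table 6 forgets enrolment loss, or 416 is a miscalculation that shortens the times.* Steps 1 and 2 show otherwise. With 1,800 kept, 276 evaluable cases exceed the 259 needed. No stopping rule is tied to 416; the interim trigger is about 170 accrued cases.
- *VE 50% cannot be reached in 4 years.* At a steady rate-based count the overrun is 0.1-0.3 year, and the protocol summary plans at least 4 years. The result also depends on alpha. SAP section 7 drops the interim VE analysis and SAP 6.1.1.2 uses two-sided 0.05 for the matched analyses, while SAP 2.2 still cites 0.025. At 0.05, VE 50% needs 214 cases, or 3.4-3.6 years at 1,539 to 1,638 admissions.
- *The 10% coverage scenario is out of reach.* Row 9 needs 4,162 / 0.64 = 6,503 CAP admissions, which is 3.97 years at a steady 1,638. The apparent 251 against 252 arises because a 1:10 ratio implies 9.1% VT, not 9%.

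Section 12.1.2 also warns that lower accrual would lengthen enrolment. That covers uncertainty in general, but it does not explain where 1,800 comes from.

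**Conclusion.** The point holds as a reconciliation problem with a conditional consequence. The stated basis of the forecast gives about 1,540 to 1,640 admissions a year against 1,800 used. If the rate-based count is right, Table 6's times lengthen by about 10-17%: 2.7-2.8 years for the base case and 4.1-4.3 for VE 50%, at Table 6's alpha of 2.5% and a steady count. The base case is reached within 4 years in every variant examined. The VE 50% claim turns on whether admissions reach about 1,670 a year and on the alpha finally used.

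Separately, and whatever the true count, 648 and 416 are not comparable with the needed cases in Table 6, and the Enrolled column covers only one of several exclusions.

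The figures assume the protocol's 9% VT share, 36% immunocompromised, 70% enrolment and 95% valid specimens. The phased figures also assume that Table 3's two catchments describe the first 11 months. Non-resident enrolment would raise accrual by an amount the documents do not give.

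**What to change.** In Protocol 12.1.2, including Table 6 and its footnote d:

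1. Give the source, year, codes and hospitals behind 1,800, and reconcile it with Table 4, section 9.1 and Table 3. Otherwise show Years to Enroll for 1,540 to 1,800 admissions a year, with the third hospital phased in from February 2022.
2. Label 648 and 416 as admissions before enrolment and specimen loss. Add the evaluable counts: about 431 and 276 at 1,800 a year, and 368-392 and 236-251 at the rate-based count.
3. State that Enrolled covers only the 5% specimen loss, and add an allowance for the other exclusions in 12.1.3.1, marked as an assumption.
4. Say that reaching VE 50% within 4 years requires about 1,670 or more admissions a year at alpha 0.025, and state which alpha applies now that the SAP has no interim VE analysis.

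While that text is open, the 5,400 enrolled in 4 years should also be checked: 1,800 × 0.70 × 4 = 5,040.

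The cost is wording and table figures in the next amendment. The design and procedures do not change. The stated timelines may become less favourable, and an explicit allowance under item 3 would raise the planned enrolment number.
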